1.0 PURPOSE

1.1 Name and Intended Use

The procedure used in this study is called the MyEllevate® procedure.

The intended purpose of the MyEllevate® procedure used in this study is to assess the safety and efficacy of the procedure for soft tissue approximation and elevation of sub dermis and underlying muscle of the submentum & jawline.

1.2 Objectives

1. Primary Objective:
 - Safety assessment through the collection of Adverse Events.
2. Optional Assessments:
 - Collection of digital 2-D and/or 3-D photography.
 - Photographic evaluation with correct identification of pre-treatment images when compared to the 30 and 90 day follow-up images performed by blinded reviewers.
 - Principle Investigator assessment using the Global Aesthetic Improvement Scale (PGAIS) at the 30 and 90 day follow up visit.
 - Subject assessment using the Global Aesthetic Improvement Scale (SGAIS) at the 30 and 90 day follow up visit.
 - Subject satisfaction rates at the 30 and 90 day follow-up visit.
3. Additional Safety Objectives:
 - Collection of Discomfort/Pain Scores

1.3 Duration of the Investigation

The sponsor anticipates that all subjects can be enrolled within 3 months. If subject participates in all required visits, then the subject's participation in this study may last up to 4 months. It is anticipated that it will take approximately 3 months to analyze the data collected during this study. The total duration of this study is anticipated to last approximately 10 months.

2.0 PROTOCOL

2.1 Protocol Methodology and Analysis

Methodology:

Subjects are to be enrolled in this clinical study if they are a healthy male or female between the age of 18 – 65. Up to 10 subjects will be enrolled at 2 study centers. All subjects will attend a screening/pre-procedure visit which may be performed on the same day as the procedure visit but no more than 30 days prior to their procedure. Subjects will receive a phone call 1 week (1-10 days) after their procedure to record side effects. Subjects will return for follow up visits at 30 and 90 days post their procedure for efficacy and side effects assessments.

An unscheduled visit or phone call may be performed at any time during the study at the request of the subject or as deemed necessary by the site Investigator.

Analysis:

Upcoming generations are proving to have an interest in aesthetic treatments and will drive demand for innovated products, procedures, and practice design.ⁱ Due to this shift in patient base, practices need to evolve to adapt to the newer generational ideologies. There have been rapid advances in minimally invasive neck rejuvenation over the past few years and using innovative procedure offers great promise to our aging population. The MyEllevate® procedure used for soft tissue approximation and elevation of sub dermis and underlying muscle of the submentum and jawline needs to be further investigated to collect additional data to support the safety and efficacy of the procedure.

Relevance:

According to the 2020 Plastic Surgery Statistics Report, neck lifts are in the top 10 cosmetic surgical procedures performed, with over 160,000 surgeries performed despite the average 8.1 weeks most surgeons stopped performing elective surgical procedures for due to the COVID-19 pandemic.ⁱⁱ There was also a survey conducted by American Society of Plastic Surgeons (ASPS) during the pandemic which found that 11% of women surveyed indicated they are more interested in cosmetic plastic surgery or non-surgical procedures now than before COVID-19.ⁱⁱⁱ Currently, the comparable procedures and/or treatments available for visible platysma bands, glands and/or sagging in the submentum, jawline and/or neck include, but not limited to, NeckTite and a neck lift. The limitations of current products on the market include different side effect profiles and how invasive the procedure is.

Testability:

The MyEllevate® device, had been previously cleared for use for use in soft tissue approximation and elevation of subdermis and underlying muscle. (FDA 510(k) K091061). This study will utilize the collection of photography and side effect data to assess the safety and efficacy of the procedure.

Compatibility:

Due to the increasing demand for aesthetic procedures, there is a need to treat visible platysma bands, glands and/or sagging in the submentum, jawline and/or neck in its earlier stages to optimize treatment outcomes. As a subject gets older or the condition worsens, their treatment may need to be more aggressive to get their body to respond the same way that a younger subject or less severe case may be able to respond.

Predictive power:

Although previous studies found this procedure to be effective for neck rejuvenation with few complications^{iv}, data collection of the side effect profile of this procedure needs to be further investigated to confirm the safety of this approach. Assuming that there is significant improvement, it would be appropriate to expect results in different areas where other procedures and devices have significant results.

2.2 Protocol Study Design

This is a prospective, open label, multi-center clinical study to collect safety and efficacy data on the MyEllevate® device.

2.3 Subject Selection Criteria

Subjects will meet the criteria described below:

Inclusion Criteria:

- A healthy male or female between the age of 18 – 65.
- Must have any or all the following: visible platysma bands, glands and/or sagging in the submentum, jawline and/or neck.
- Reads and understands English.
- Understands and accepts obligation not to receive any other procedures on the treatment area through the length of the study.
- Understands and accepts the obligation and is logistically able to be present for all visits.
- Is willing to comply with all requirements of the study and sign the informed consent document.

Exclusion Criteria:

- Is pregnant or of childbearing potential and not using medically effective birth control, or has been pregnant in the last 3 months, currently breast feeding or planning a pregnancy during the study.
- Is currently enrolled in an investigational drug or device trial, or has received an investigational drug or been treated with an investigational device within in the area to be treated 6 months (or at the discretion of the Investigator) prior to entering this study.
- Have received any treatments or procedures (including injectables such as Botox or fillers) in the area to be treated at least 4 months prior to treatment.
- Take antiplatelets, anticoagulants, thrombolytics, or anti-inflammatories.
- Have an active localized or systemic infection.
- Have an open wound in area being treated.
- Have a significant systemic illness or an illness localized in area being treated.
- Have had recent surgeries or problems in the treatment area (e.g. neck fracture, neck sprain, pinched nerve, spondylosis, arthritis in the neck).
- Have a history of thrombophlebitis.
- Have a history of heart failure or kidney disease.
- Have a history of allergic reaction or intolerance to the anesthesia used during the procedure.
- Have a history of poor wound healing.
- Have a history of poor circulation.
- Have a systemic autoimmune disease known to impair wound healing.
- Have a history of keloid formation.
- Currently enrolled in an investigational drug or device trial, or has received an investigational drug or been treated with an investigational device within the area to be treated 6 months (or at the discretion of the Investigator) prior to entering this study.
- Has any condition or is in a situation which in the investigators opinion may put the subject at significant risk, may confound study results or may interfere significantly with the subject's participation.

Be sure to list all concomitant medications taken or procedures performed before, during and after the trial

Subjects will be recruited for the study through the existing patient database and may also be recruited through advertisements.

Subject populations will not be eligible to participate in the study if they are vulnerable populations such as children, pregnant women, prisoners, institutionalized individuals, and any persons requiring a legally authorized representative as part of the consenting process.

Subject population characteristics that will not be eligible to participate in the study include non-English speaking individuals and people who cannot read or comprehend English. Employees of the Investigator will be participating in the study.

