2.4 Screening

Subjects will be asked questions about their medical history, may have a limited physical and their inclusion/exclusion criteria will be verified. Discontinuation of any concomitant medications (such as aspirin, NSAIDS, herbals, vitamins, diet pills) will be discussed, and post treatment instruction will be reviewed with the subject.

Procedure for the Limited Physical Exam:

If the investigator determines that a limited exam is necessary, the exam will be like a basic annual physical exam performed by a primary care doctor to determine general overall health. The limited medical exam may include all or any of the following; vital signs such as blood pressure, heart rate, respiratory rate and body temperature, general appearance, listening to the heart, lungs and abdomen with a stethoscope, head and neck exam, in addition to examining the throat, tonsils, teeth, ears, eyes and nose as well as a neurological exam such as testing muscle strength, reflexes, balance, sensory changes of the extremities and mental state.

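### As worded, the prior-treatment exclusion bars people treated in the area 4 or more months ago and admits people treated only within the last 4 months, the reverse of a washout

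*Combined protocol and SAP*

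**What the plan says.** The exclusion list in Section 2.3 (Subject Selection Criteria) contains an item that opens "Have received any treatments or procedures" and continues, in and after a parenthesis, "including injectables such as Botox or fillers) in the area to be treated at least 4 months prior to treatment". Meeting this condition makes a person ineligible.

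Other text bears on earlier or concurrent treatment of the area:

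- An inclusion criterion in the same section covers the study period: "Understands and accepts obligation not to receive any other procedures on the treatment area through the length of the study".
- The pregnancy exclusion is written as a look-back: "has been pregnant in the last 3 months".
- The investigational drug and device exclusion, which appears twice, seems to look back 6 months, although its wording is also garbled.
- A further exclusion reads "Have had recent surgeries or problems in the treatment area". It does not define how recent.
- A closing clause excludes any condition or situation "which in the investigators opinion may put the subject at significant risk, may confound study results".
- Section 2.3 also instructs: "Be sure to list all concomitant medications taken or procedures performed before, during and after the trial".

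Section 2.4 (Screening) states that the "inclusion/exclusion criteria will be verified". No other section restates the prior-treatment rule or sets an interval for earlier non-investigational treatment.

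**The concern.** In ordinary English, *at least 4 months prior* means 4 months or longer before. A washout exclusion needs the opposite direction: treatment less than 4 months before. As an operative rule, the line therefore turns away people whose treatment lies furthest in the past and lets in people treated most recently.

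Two things are at stake.

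- **If a center applies the line literally**, a person treated only recently can enter. Section 2.2 describes an open-label study and no control arm is described. Section 2.13 has the Global Aesthetic Improvement Scale (GAIS) rated against the original condition and photographs compared with pre-treatment images. A recent treatment whose effect is still changing would be mixed with the effect of the procedure at 30 and 90 days. It could also blur the attribution of local adverse events.
- **If a center applies the probable intent**, enrolling someone treated only 4 or more months ago departs from the written criterion. Section 21.0 permits no deviation without sponsor approval outside a medical emergency, and Section 15.0 requires IRB approval of requested deviations that the sponsor accepts.

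Section 2.1 plans 2 centers, which could apply the line in opposite directions.

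**Working it through.** The plan states no figure to reproduce. The check is a logical one on the wording.

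**Inputs.** The interval is T = 4 months, from the exclusion item in Section 2.3. Let t be the time from a prior treatment of the area to the study procedure. The item counts any treatment or procedure and sets no upper limit on t.

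**The two rules.**

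- Literal rule: exclude if any prior treatment has t ≥ T.
- Look-back rule: exclude if any prior treatment has t < T.

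**Application to every possible history.**

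| History of treatment in the area | Example | Literal rule | Look-back rule | Agree? |
|---|---|---|---|---|
| None | – | eligible | eligible | yes |
| Only t < T | 1 month ago | eligible | excluded | no |
| Only t ≥ T | 10 years ago | excluded | eligible | no |
| Both | 1 and 6 months ago | excluded | excluded | yes |

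The rules disagree on 2 of the 4 histories. They give opposite answers for everyone who has been treated and whose treatments all fall on one side of T. They agree for people never treated and for people treated on both sides. This counts types of history, not subjects. The documents do not say how candidates are distributed over the four rows.

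**Does another criterion close the gap for the second row?** Take a person whose only prior treatment is a marketed injectable 1 month earlier, the kind of treatment the item itself names.

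1. The inclusion criterion on other procedures looks forward from entry. It does not reach earlier treatment.
2. The 6-month items concern investigational products only.
3. The recent-surgeries item leaves *recent* undefined. Its examples are fractures, sprains, and nerve and joint problems, not injectables.
4. The investigator-opinion clause could exclude this person, but it is discretionary and sets no interval.
5. Listing earlier procedures records the exposure without deciding eligibility.

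None of these clearly bars the person. For the third row nothing is available either: no other criterion can readmit someone whom an exclusion has removed.

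**Weight of one subject.** Section 2.15.2 gives a total of 10. If all 10 are enrolled and assessed, one misdirected eligibility decision concerns 1/10 = 10% of the sample.

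**The case against.** The best defence is that the intent is obvious. The pregnancy and investigational-product items look back, and naming injectables makes sense mainly as a recency rule. Sections 3.2, 3.3 and 5.0 provide for an experienced investigator, training on the protocol, and sponsor training and monitoring of the site. Such an investigator is unlikely to turn away everyone treated years ago, and can use the confounding clause to exclude a recently treated person without any deviation.

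The consequences can also be called modest. Section 1.2 lists the photographic, GAIS and satisfaction assessments as optional. For the primary objective, adverse events, Section 2.15.6 plans summaries only, earlier procedures are to be listed, and the relatedness definitions in Section 14.0 name therapeutic interventions as an alternative cause. Section 2.4 says that criteria are verified but does not say how strictly they are read, and the eligibility form is not among the documents.

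Most of this stands as mitigation. It makes literal application less likely and limits the effect on the primary objective. It does not correct the rule. The confounding clause depends on each investigator's judgement, and reliance on intent leaves sites departing from the text whenever they enrol someone treated only longer ago. A rule that works only when read against its own words still needs to be rewritten.

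**Conclusion.** The concern holds. The prior-treatment exclusion is wrong as written: it runs in the opposite direction to a washout for every treated person whose treatments all lie on one side of 4 months. It is a drafting error in an operative eligibility rule, not a disputed design choice, and it should be fixed.

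The effect shown is on eligibility alone. No bias in the results is quantified, because the documents do not give the number of candidates in each history or the size and direction of any residual treatment effect. Any confounding would fall mainly on the optional 30- and 90-day assessments, with a smaller effect on adverse event attribution.

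The conclusion rests on the ordinary meaning of *at least* and on the absence of any correcting text elsewhere in the protocol. That a look-back was intended is an inference from the neighbouring items, so the sponsor has to confirm it.

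**What to change.** 1. The sponsor confirms which direction was intended. If it is a look-back, replace *at least* with *within* in the Section 2.3 item and keep the sponsor's own stated interval.
2. Bring the eligibility form into line and inform both centers.
3. Recheck people already screened, in both directions: those turned away only for older treatment, and those admitted with only recent treatment. The first group can be rechecked only where screening records exist. Section 2.5 assigns identification numbers only to people who met all criteria, and no screening log is described.
4. Flag any enrolled subject treated inside the interval in the adverse event and assessment listings.

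The cost is one phrase in a protocol amendment with the written IRB approval that Section 21.0 requires, an edit to the eligibility form, and a short review of screening records and listings for a study of up to 10 subjects. Visits and sample size do not change.

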2.4 Screening

Subjects will be asked questions about their medical history, may have a limited physical and their inclusion/exclusion criteria will be verified. Discontinuation of any concomitant medications (such as aspirin, NSAIDS, herbals, vitamins, diet pills) will be discussed, and post treatment instruction will be reviewed with the subject.

Procedure for the Limited Physical Exam:

If the investigator determines that a limited exam is necessary, the exam will be like a basic annual physical exam performed by a primary care doctor to determine general overall health. The limited medical exam may include all or any of the following; vital signs such as blood pressure, heart rate, respiratory rate and body temperature, general appearance, listening to the heart, lungs and abdomen with a stethoscope, head and neck exam, in addition to examining the throat, tonsils, teeth, ears, eyes and nose as well as a neurological exam such as testing muscle strength, reflexes, balance, sensory changes of the extremities and mental state.

2.5 Informed Consent Process and Enrollment

Subjects will be asked to review the post treatment instructions prior to signing the informed consent form and their involvement in the study. The Investigator will be responsible for assuring the subject understands how to use each support device (neck brace and chin strap) and understands all requirements of the post treatment instructions. Subjects will be informed of site's COVID-19 procedures that adhere to federal and state guidelines at this time. Subjects who sign the informed consent will be screened to confirm eligibility and, if eligible, will be assigned a subject identification number. Subjects will be de-identified through their subject identification number, which will be stored in a secure location. Subject identification numbers will be generated chronologically and assigned only to subjects who have met all the study selection criteria and have signed the informed consent form. The informed consent will be obtained prior to a subject's involvement in any study related procedures. A subject will be considered enrolled in the study once they have signed the informed consent form.

The following post treatment instructions will be reviewed:

- Resting:

When sleeping or lying down, should be positioned at a minimum incline of 45 degrees for first 10 days of recovery.

- Chin strap:
Wear at all times for 3 days.
- Neck brace:
Wear for 10 days while reading/watching TV/working on computer/looking down at phone.
Secure neck brace every night before sleeping (to always keep head in neutral position).
- Icing:
Remove dressings to ice the procedure area using frozen peas for 20 minutes every hour while awake. Don't apply directly on tissue use protective barrier i.e., paper towel.
- Bathing/ Hygiene:
May shower, using mild soaps or baby shampoo (not streaming directly on face, shower with back facing shower head). No shaving for 10 days but trimming or clipping hair is acceptable.
- Avoid all alcohol consumption for 2 weeks after procedure.

2.6 Pre-Treatment Procedures

If the subject is of childbearing potential (i.e. females not post-menopausal or not surgically sterile), pregnancy verification will be required prior to their MyEllevate® procedure. Pregnancy verification will be performed by asking the subject if they are pregnant, the date of their last menstrual cycle, and be required to perform a urine pregnancy test at the site. A urine pregnancy test may also be conducted at the Investigator/clinician's discretion at any time during the study at the study center. If a urine pregnancy test is conducted, then a negative result must be obtained.

Urine Pregnancy Test Procedure:

1. A urine sample is tested mid-stream or by cup sample with an indicator stick.
2. Negative results are indicated on the indicator stick.

- Photographs will be taken prior to the procedure.

2.7 Treatment Procedures

- The defined study area will be identified and may be marked with a surgical marker.
- A local tumescent anesthetic, such as lidocaine, will be injected to the area prior to the procedure.
- The MyEllevate® device will be used in accordance with the Instructions for Use (IFU) manual.
- Subjects will be asked to report the general level of treatment discomfort/pain on a scale of 0 (none) to 10 (maximum intolerable pain).
- Photographs may be taken during treatment.

2.8 Post Treatment Procedures

- Adverse events will be documented after treatment.
- Photographs may be taken post treatment.
- Post treatment instructions will be reviewed with the subject.

- A diary will be handed to the subject to complete to track adverse events and when they were able to return to normal activities. They will need to bring this diary to all of their post procedure visits.

2.8 Follow Up

- Subjects will receive a phone call 1 week (1-10 days) after the procedure to record side effects.
- Subjects will return for follow up visits at 30 and 90 days after the procedure.
- Photographs will be taken and adverse events, and subject assessment (Subject Global Aesthetic Improvement Scale), and satisfaction will be documented.
- Any subject affected by COVID-19 that is not able to attend their follow up visits to complete the study will be asked to return to the site for a final follow up visit within 1 year of last treatment.

Some subjects may have an incomplete response or no response by the end of the study. At the end of the study, treatments/procedures using an FDA approved/cleared treatment method may be discussed with the subject and obtained at the cost of the subject.

2.10 Unscheduled Visits

An unscheduled visit may be performed at any time during the study at the subject's request or as deemed necessary by the site Investigator. The date and reason for the unscheduled visit will be recorded in the source documentation.

